3.5. Stratification, Randomization, and Blinding/Masking

Arm dominance may affect the spread of ShA9 to the contralateral arm; therefore, the design will stratify by arm dominance, with the dominant arm being the right arm for right-handed participants, and the left arm for left-handed participants. A minimum of 13 participants with *S. aureus* colonized lesions on their ventral arms and a minimum of 7 participants with *S. aureus* negative lesions on their ventral arms will be randomized to one of two treatment groups: 1) ShA9 dominant and placebo non-dominant or 2) ShA9 non-dominant and placebo dominant. It is anticipated that enrollment will be higher for right-handed participants as that is the more dominant arm in the general population; enrollment will not target equal numbers of right-handed and left-handed participants. Randomization will be performed centrally at the Statistical and Clinical Coordinating Center (SACCC) using a stratified randomization design.

This is an open-label study, as all participants will receive active and placebo treatment. However, investigators, all investigational site staff, including those responsible for preparing/administering the investigational product, and all participants in this study will be blinded as to which arm received which treatment. Laboratory staff performing the mechanistic assays will be unblinded to which arm received which treatment, to ensure the correct dilutions can be applied to each sample prior to completing assays for quantification of live bacteria by culture (*S. aureus* and CoNS) and bacterial DNA (*S. hominis* A9) by qPCR (Refer to [Section 9](#)).

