7.3. Prohibited Medications/Therapies

Participants are prohibited from using the following medications/therapies:

- Topical AD treatments (including steroids and topical calcineurin inhibitors) on the ventral arms where treatment is applied and the designated swabbing area on the face; Use of topical steroids on other areas is permitted per investigator discretion, as described in [Section 7.1.2](#).
- Any lotions, ointments or creams, including prescription moisturizers classified as a medical device (e.g., Atopiclair®, MimyX®, Epiceram®, etc.), other than Cetaphil® lotion (provided by the research clinic) on the ventral arms where treatment is applied and the designated swabbing area on the face; Use on other areas is permitted
- Oral or topical antibiotics
- Bleach baths
- Oral or injectable AD therapies (steroids, immunosuppressive therapies, biologics)
- Phototherapy (such as NBUVB, UVB, UVA1, PUVA) or tanning beds

After the date of their CoNS falling below baseline density measured before application of ShA9 + 100 CFU/cm², the participant will be allowed to use prohibited medications/therapies, as needed. Use of medications/therapies will be recorded on the concomitant medications case report form (CRF).

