8.3. Pre-treatment Visit (Day -7 ± 1 Day)

Screened and eligible participants will be invited to complete the Pre-treatment Visit. If a participant meets all required washout periods for medications/therapies during their Screening Visit, they may complete the Pre-treatment Visit on the same day of the Screening Visit. The Pre-treatment Visit must be completed 7 days (\pm 1 Day) prior to the Day 0 Visit. During this visit, participants will have their initial skin swabs collected for the assessment of live bacteria by culture (*S. aureus* and CoNS) and bacterial DNA (*S. hominis* A9) by qPCR.

The following procedures, assessments, and laboratory measures will be conducted at this Pre-treatment Visit:

- Interim medical history and physical exam, including assessment of AD severity (L-EASI, SCORAD, and local Pruritus NRS) by study physician or other qualified medical professional (if conducted on a different day than the Screening Visit)
- Pregnancy status of participant and partner of participant, as applicable (if conducted on a different day than the Screening Visit)
- Assessment of concomitant medications (if conducted on a different day than the Screening Visit)
- Vital signs (if conducted on a different day than the Screening Visit)
- Identification of measured lesional and non-lesional sites on the participant's ventral arms, including photographs, and skin swab collection, to assess live bacteria by CFU and bacterial DNA by qPCR. Two lesional and two non-lesional swabs will be collected from each arm (8 swabs total).
- Assessment of AEs

During the Pre-treatment Visit, participants will be given Cetaphil® lotion and Dove moisturizing soap. Participants will be instructed to apply a thin layer of Cetaphil® lotion to each arm, twice a day for approximately 1 week (Pre-treatment

Visit until Treatment Visit) and to use the soap when they shower, avoiding the arms. At the conclusion of the visit, participants will be given instructions regarding restrictions on bathing/showering, exercise, and use of emollient. Participants will be instructed to refrain from swimming in chlorinated pools and hot tubs and to refrain from the use of prohibited medications, for the duration of their study participation. Female subjects of child-bearing potential will be instructed to use an effective method of birth control or abstinence.

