At the conclusion of this visit, participants will be reminded to use Dove moisturizing soap, whenever they shower, but to avoid the arms, until after their last in-clinic visit is complete. Participants will be allowed to use Cetaphil® lotion to moisturize if necessary. Participants will be given instructions regarding restrictions on bathing/showering, exercise, and use of emollient. Participants will be reminded to refrain from swimming in chlorinated pools and hot tubs and to refrain from the use of prohibited medications, for the duration of their study participation. Participants will be asked to try to restrict pets from licking the treated areas. Female subjects of child-bearing potential will be instructed to use an effective method of birth control or abstinence.

Participants will be given a handcard describing the symptoms of skin and systemic infections and will be told to contact the research clinic if they experience any of the listed symptoms. The participants will be instructed to take the handcard with them should they seek medical care at another facility. The handcard will state that the patient is

currently in a study involving the application of non-pathogenic bacteria to the skin and will instruct them to call the research site if an infection of the skin or blood is suspected.

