8.5. Follow-Up Visits (24 Hour and Days 3, 10, 17 and 24)

After the Treatment Visit, participants will be asked to return to the clinic for a follow up 24 Hours after the Day 0 Visit and on Days 3 (\pm 1 day), 10 (\pm 1 day), 17 (\pm 2 days), and 24 (\pm 2 days). The purpose of the follow-up visits is to assess *S. aureus* and CoNS bacteria abundance and AEs.

The following procedures, assessments, and laboratory measures will be conducted at each visit:

- Assessment of AEs
- Assessment of AD severity (L-EASI, SCORAD, and local Pruritus NRS) by study physician or other qualified medical professional
- Pregnancy status of participant and partner of participant, as applicable
- Assessment of concomitant medications
- Vital Signs
- Skin Swab Collections, (lesional and non-lesional) from the ventral arms, to assess live bacteria by CFU and bacterial DNA by qPCR and non-lesional skin swab collection from the participant's face for the assessment of ShA9 spread. Two lesional and two non-lesional swabs will be collected from each ventral arm, and two additional non-lesional swabs will be collected from the face (10 swabs total).
- Lesional skin swabs taken at the last Follow-Up Visit will also be analyzed for antibiotic sensitivity to penicillin G, tetracycline, and erythromycin.

At the conclusion of each visit, participants will be reminded to use Dove moisturizing soap, whenever they shower, but to avoid the arms, until after their last in-clinic visit is complete. Participants will be given instructions regarding restrictions on bathing/showering, exercise, and use of emollient. Participants will be reminded to refrain from swimming in chlorinated pools and to refrain from the use of prohibited medications. Female participants of childbearing potential will be instructed to use an effective method of birth control or abstinence.

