Upon completion of the Day 3 Visit, a participant will be notified prior to their next scheduled follow-up visit if they need to return to the clinic. A participant will not be required to complete the remaining follow up clinic visits (Day 10 through Day 24) if the lesional swabs from both arms collected at their most recent prior visit are CoNS negative, defined as below baseline density measured before application of ShA9 + 100 CFU/cm². The lesional skin swabs taken at the last completed Follow-Up Visit will be used in analysis for antibiotic sensitivity to penicillin G, tetracycline, and erythromycin. Once a participant completes his/her required follow up clinic visits, he/she may resume prohibited medications as described in [Section 7.3](#), as needed, and may use his/her choice of soap and emollient.

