11.1. Participant Completion

Participant participation will be defined as complete at the conclusion of the Day 31 End of Study Phone Visit.

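### Protocol V2.0 ends the ban on prohibited therapies at three different points, and the SAP prespecifies no flag for such use before the last clinic visit

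*Protocol*

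**What the plan says.** Four parts of the protocol bear on when the ban ends.

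- **Section 7.3** lists the prohibited therapies, including oral and topical antibiotics, bleach baths and topical AD treatments on the arms. It then says that after the date on which the participant's CoNS falls below baseline + 100 CFU/cm², "the participant will be allowed to use prohibited medications/therapies, as needed". It names no arm, skin site or visit. Use is recorded on the concomitant-medication CRF.
- **Sections 8.3 and 8.4** tell participants "to refrain from the use of prohibited medications, for the duration of their study participation". Section 11.1 fixes the end of participation: "Participant participation will be defined as complete at the conclusion of the Day 31 End of Study Phone Visit".
- **Section 8.5** says: "Once a participant completes his/her required follow up clinic visits, he/she may resume prohibited medications", and refers back to 7.3. After Day 3, the remaining visits are waived "if the lesional swabs from both arms collected at their most recent prior visit are CoNS negative".
- **Section 8.5** also sets a reminder at the end of each follow-up visit: "Participants will be reminded to refrain from swimming in chlorinated pools and to refrain from the use of prohibited medications".

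The SAP handles medications and deviations in general terms. Section 9.1 classes medications as prior, concomitant or after study treatment, by reference to the single treatment date. Section 4.3 limits per-protocol exclusions to unapproved product or wrong dose. Section 7.1.3 includes all data whatever the time of assessment. Section 7.3.1 censors only participants who never reach elimination. Sections 7.4.2 and 7.5.2 give no rule for prohibited therapy.

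**The concern.** A site that follows 7.3 as written could release a participant from the ban while 8.5 still requires clinic visits. Those visits supply the later non-lesional swabs (secondary endpoint 1) and the L-EASI, SCORAD and pruritus scores (exploratory endpoints 6-8). The last of them supplies the lesional swab for antibiotic sensitivity (exploratory endpoint 9).

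The released therapies can act on these outcomes. Section 7.4 lists ShA9 as sensitive to mupirocin and minocycline, the protocol's own first-line antibiotics for infection, so antibiotic use could shorten apparent non-lesional survival. It could also change the proportion of sensitive CoNS at the last swab. Arm steroids could improve the last-visit severity scores.

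Use that 7.3 permits might not be logged as a deviation, because Section 15.1 defines a deviation as a departure from the study design or procedures. The SAP text then has no prespecified way to separate results obtained before and after such use.

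**Working it through.** The plan gives no figure on this point, so the check sets the rules side by side and applies them to cases.

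**How far apart the three end points can be.** Inputs are the 15-minute first swab (Protocol 8.4) and the visit windows in Appendix B. Suppose the first value below threshold is at 15 minutes on Day 0.

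| Rule | Ban ends | Time after the first low value |
|---|---|---|
| 7.3, literal | Day 0 | 0 |
| 8.5, earliest | Day 3 ± 1 | 3 − 1 = 2 to 3 + 1 = 4 days |
| 8.5, latest | Day 24 ± 2 | 24 − 2 = 22 to 24 + 2 = 26 days |
| 8.3/8.4 with 11.1 | Day 31 ± 7 | 31 − 7 = 24 to 31 + 7 = 38 days |

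For one participant the rules can therefore differ by days to weeks.

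**Where the difference can affect data.**

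1. *Both arms' lesional swabs are first below threshold at the same follow-up visit, Day 3 or later.* Sections 7.3 and 8.5 then agree in effect, because no further clinic visit is required. Sections 8.3/8.4 would still ban use to Day 31, but no swab or severity score remains due.
2. *One arm is below threshold and the other is not*, for example the treated arm has cleared and the placebo arm has not. Section 8.5 still requires the next visit. Section 7.3 can be read as having ended the ban, because it does not say which arm counts.
3. *An early low value rebounds*, for example below threshold at 6 hours and above it at Day 3. Section 7.3 turns on the date of falling below, which has passed. Section 8.5 turns on the most recent visit, which is above threshold, so visits continue. SAP 7.3.1 counts the first low value as the event.
4. *Low before Day 3 without rebound.* The Day 3 visit is still required, so a short gap exists here too.

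Cases 2 and 3 are the main exposed cases.

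**Which endpoints are exposed.** If 7.3 means treated-arm lesional skin, the primary event comes before the permission, so time to first elimination is largely unaffected. Non-lesional elimination may come later than lesional elimination, and exploratory endpoints 6-9 are taken at the last clinic visit, so these can follow permitted use.

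**What the SAP would pick up.** A start date after Day 0 places a medication relative to treatment under SAP 9.1. It does not place it relative to the first low value or the last clinic visit, and there is no prohibited category. The per-protocol sample would not change, because its exclusions concern study product only. The deviation listing in SAP 6.1 carries dates, but it depends on the site treating the use as a deviation. A site that judges by 8.4 or 8.5 would do so; one that judges by 7.3 might not.

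**The case against.** The strongest reply is that 8.5 is the working rule and 7.3 only needs tidying. Sections 3.1 and 8.5 consistently define CoNS negative as lesional swabs from both arms, which is a natural reading of 7.3 as well. On that reading case 2 disappears and mainly the rebound case is left. Participants are reminded of the ban at each follow-up visit, and the only described notice about stopping visits comes after Day 3. Swabs are frozen until analysis (9.2). Under 3.5, site staff and "all participants in this study will be blinded as to which arm received which treatment", so the site could not readily apply a treated-arm trigger itself. Section 11.2 allows withdrawal when prohibited therapy would interfere with the endpoints. All of this stands and makes exposure less likely. It does not make the sections agree, since 8.5 refers to 7.3 for a rule that 7.3 states differently.

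Three stronger readings are tempting, and the documents do not support them.

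- *A percentage bias in the non-lesional hazard.* With 13 *S. aureus* positive participants, one altered event time could matter. Any figure, however, needs each participant's non-lesional follow-up and the frequency of use. Section 8.5 can end visits at Day 3 on lesional results alone, whatever the non-lesional result, and neither the number leaving early nor the frequency of use is given.
- *The outputs will hide such use.* SAP Section 2 places table and listing specifications in separate documents and allows additional analyses. SAP 7.2 plans swab listings by participant, and 9.1 uses medication dates. Only the absence of a prespecified flag in the SAP text can be asserted.
- *The primary endpoint is compromised.* That requires reading 7.3 as any arm or any skin site, which the both-arm lesional definition elsewhere makes unlikely.

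**Conclusion.** The concern holds as a real inconsistency of minor to moderate importance. Protocol Version 2.0 ends the ban at three different points. The SAP text neither flags prohibited therapy before the last in-clinic visit nor says how to handle results that follow it. The exposed outcomes are secondary endpoint 1 and exploratory endpoints 6-9, mainly when one arm has cleared and the other has not, or after an early low value that rebounds.

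No size is given for the effect on results, because the documents give neither the frequency of these cases nor that of use within them. The conclusion that the primary endpoint is largely unaffected rests on 7.3 meaning treated-arm lesional skin, or both arms' lesional skin, where the primary event also comes first.

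One limit applies throughout: the supplied protocol is Version 2.0 (Appendix B footer), while the SAP carries the Version 3.0 synopsis, so 7.3 may since have changed. The gap in the SAP would remain even then.

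**What to change.** 1. Check 7.3 in protocol Version 3.0. If it is unchanged, amend 7.3 and 8.3/8.4 to match 8.5: prohibited therapies, except medically necessary rescue, resume only after the last required in-clinic swab and assessment.
2. In the SAP, flag prohibited or rescue therapy by date between Day 0 and the last in-clinic visit, using the concomitant-medication CRF.
3. Keep the all-data analysis. If any such use occurs, show a sensitivity result beside it that censors non-lesional time to elimination at first use and takes the last pre-use score for exploratory endpoints 6-8. State that this censoring may be informative.
4. For exploratory endpoint 9, only flag or exclude affected participants. Section 9.5 plans sensitivity testing at baseline and the last follow-up visit only, so no intermediate result is available.

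The cost is a wording change, a slightly longer restriction for some participants than 7.3 alone implies, and one small conditional analysis. The dates are already collected, and no extra plating is needed.

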7.4. Rescue Medications

If infection occurs, treatment will include topical and/or oral antibiotics depending on the severity of the infection clinically, and Cetaphil® lotion (for irritation and dryness). The antibiotic sensitivity profile of *Staphylococcus hominis* A9, includes sensitivity to ampicillin-sulbactam, cefazolin, cefoxitin, clindamycin, daptomycin, levofloxacin, linezolid, minocycline, moxifloxacin, mupirocin, nitrofurantoin, oxacillin, rifampin, trimethoprim-sulfamethoxazole, and vancomycin; intermediate sensitivity to doxycycline; and resistance to erythromycin, penicillin G and tetracycline. The antibiotic of choice will depend on the individual participant's medical history, including any possible contraindications to certain medications due to allergies or other concomitant medication use, but mupirocin will be the first line topical antibiotic of choice, and minocycline will be the first line oral antibiotic, followed by first generation cephalosporins, trimethoprim-sulfamethoxazole or rifampin. Contact allergic reactions to Cetaphil lotion or glycerol will be treated with mid-potency topical steroids, such as fluocinonide ointment 0.05%.

8. Study Procedures

A summary of complete study procedures is included in Appendix B Schedule of Events. To ensure participant safety, participants will be asked to comply with UCSD's current institutional policies and procedures related to COVID-19, which are based on recommendations from the Centers for Disease Control and Prevention when scheduling and attending their appointments.

8.1. Recruitment Visit

Potential participants will be recruited using standardized questionnaires that collect contact information and disease status related to inclusion and exclusion criteria. Participants may be recruited by phone or in person. Potential participants from UCSD departments outside of Dermatology will be identified using EPIC slicer dicer tool, then confirmed with their primary care provider to see if their patients can be approached for recruitment. Once confirmed by their primary care provider, patients will be contacted through a message on MyChart to assess their interest in participating. Those interested will then be followed up by a phone call to assess their eligibility. Those who have no obvious characteristics making them ineligible for the study and who are interested in participating will be invited to clinic to complete the Screening Visit.

8.2. Screening Visit (Day -14 to -7)

The purpose of the Screening Visit is to confirm eligibility to continue in the study. During the visit, written informed consent will be obtained from the participant prior to performing any other study procedures.

The following procedures and assessments will be conducted to determine participant eligibility:

- Collection of demographics
- Medical History and physical examination, including assessment of AD severity (IGA, L-EASI on the ventral arms, SCORAD, and local pruritus NRS) by a study physician or other qualified medical professional
- Pregnancy status and urine pregnancy test: Female participants will be asked if they are pregnant. A urine pregnancy test will be completed for all female participants of child bearing potential who do not self-report as pregnant.
- Assessment of concomitant medications
- Vital signs and growth parameters (height and weight)
- Assessment of Adverse Events (AEs)

Participants who meet inclusion and exclusion criteria including the required washout periods for medications/therapies will be considered screened and eligible. Participants who do not meet inclusion and exclusion criteria due to assessment of their concomitant medications and require a washout of 14 days or more will be required to rescreen, prior to enrolling in the study. Participants who do not wish to washout of the prohibited medications or do not meet full inclusion and exclusion criteria will be identified as screen failures and will not continue in the study.

8.3. Pre-treatment Visit (Day -7 ± 1 Day)

Screened and eligible participants will be invited to complete the Pre-treatment Visit. If a participant meets all required washout periods for medications/therapies during their Screening Visit, they may complete the Pre-treatment Visit on the same day of the Screening Visit. The Pre-treatment Visit must be completed 7 days (\pm 1 Day) prior to the Day 0 Visit. During this visit, participants will have their initial skin swabs collected for the assessment of live bacteria by culture (*S. aureus* and CoNS) and bacterial DNA (*S. hominis* A9) by qPCR.

The following procedures, assessments, and laboratory measures will be conducted at this Pre-treatment Visit:

- Interim medical history and physical exam, including assessment of AD severity (L-EASI, SCORAD, and local Pruritus NRS) by study physician or other qualified medical professional (if conducted on a different day than the Screening Visit)
- Pregnancy status of participant and partner of participant, as applicable (if conducted on a different day than the Screening Visit)
- Assessment of concomitant medications (if conducted on a different day than the Screening Visit)
- Vital signs (if conducted on a different day than the Screening Visit)
- Identification of measured lesional and non-lesional sites on the participant's ventral arms, including photographs, and skin swab collection, to assess live bacteria by CFU and bacterial DNA by qPCR. Two lesional and two non-lesional swabs will be collected from each arm (8 swabs total).
- Assessment of AEs

During the Pre-treatment Visit, participants will be given Cetaphil® lotion and Dove moisturizing soap. Participants will be instructed to apply a thin layer of Cetaphil® lotion to each arm, twice a day for approximately 1 week (Pre-treatment

Visit until Treatment Visit) and to use the soap when they shower, avoiding the arms. At the conclusion of the visit, participants will be given instructions regarding restrictions on bathing/showering, exercise, and use of emollient. Participants will be instructed to refrain from swimming in chlorinated pools and hot tubs and to refrain from the use of prohibited medications, for the duration of their study participation. Female subjects of child-bearing potential will be instructed to use an effective method of birth control or abstinence.

